9.2.1.2 Efficacy – Immunologic

Frequency of HIV-1 Gag-specific CD8+ cells by intracellular staining for IFN-gamma at baseline and at week 32 (20 weeks on sirolimus).

9.2.1.3 Efficacy – Virologic

CD4+ T-cell-associated HIV-1 RNA and plasma HIV-1 RNA by SCA at baseline and at week 32 (20 weeks on sirolimus)

9.2.2 Secondary Outcome Measures

- 9.2.2.1 CD4+ cell counts at baseline and at weeks 14, 16, 20, 24, 32 (2, 4, 8, 12, 20 weeks on sirolimus) and 44
- 9.2.2.2 HIV-1 RNA levels by conventional assay at baseline and at weeks 16, 20, 24, 32 (4, 8, 12, 20 weeks on sirolimus) and 44
- 9.2.2.3 HIV-1-specific CD4+ cell responses and HIV-1-specific CD8+ cell responses (other than gag) at baseline and at weeks 13, 16, 24, 32 (1, 4, 12, 20 weeks on sirolimus) and 44
- 9.2.2.4 T-cell activation and proliferation (% CD4+ and CD8+ cells CD38+/HLA-DR+, CD25+, PD-1+, Ki67+ and PD-L1 expression) at baseline and at weeks 13, 16, 24, 32 (1, 4, 12, 20 weeks on sirolimus) and 44
- 9.2.2.5 HIV-1 DNA levels in CD4+ cells at baseline and at weeks 13, 16, 24, 32 (1, 4, 12, 20 weeks on sirolimus) and 44

9.2.3 Exploratory Outcome Measures

- 9.2.3.1 Ex vivo flow cytometric phenotyping of activation/proliferation in CD4 and CD8 central memory (CM), transitional memory (TM), effector memory (EM) and naïve (N) populations as defined by CCR7 and CD27 expression
- 9.2.3.2 Downstream signaling of homeostatic proliferation-regulating cytokines, such as IL-7 and IL-15, in CD4 and CD8 memory subsets and correlate preferential induction of phosphorylation of STAT-5 with changes in reservoir size
- 9.2.3.3 Soluble markers including IL-6, IL-7 and IL-15
- 9.2.3.4 HIV-1 specific antibody levels, the breadth of antibody responses and B-cell phenotype, rearrangements and class switching
- 9.2.3.5 HPV typing and quantification of HPV DNA from rectal swabs at week 12 (baseline) and week 32 (20 weeks on sirolimus) and pathologic evaluation for anal dysplasia from anal Pap tests prior to and after sirolimus administration.
- 9.2.3.6 Pharmacokinetic exposure of sirolimus and ARVs in the context of concomitant use

9.2.3.7 Measurements of CMV, EBV, HSV and HHV in oral swabs prior to and after sirolimus administration

9.3 Randomization and Stratification

There is no randomization in this study. Eligible **participants** will be registered at study entry and stratified by ART regimen which determines initial dose of treatment.

9.4 Sample Size and Accrual

Regarding the assessment of safety/toxicity (see section 9.2.1.1), the sample size of 30 sirolimus-treated **participants** will provide >90% probability of observing a sirolimus-related adverse event that would occur in 8% or more of treated **participants**.

The primary efficacy analyses will evaluate paired baseline and post-sirolimus therapy immunologic and virologic measurements to detect changes; these measures are assumed stable on long-term suppressive ART (see section 2.2.6). Allowing 17% sample size adjustment for lost to follow-up and treatment discontinuation for the planned as-treated analyses (i.e., n=25 **participants** assumed evaluable), the study will have 80% power to detect a 0.59 standard deviation (SD) effect size based on a two-sided, alpha=0.05, 1-arm t-test. This effect size translates (under assumed normality) into a probability of 0.72 that a **participant** receiving sirolimus will have an observed increase in HIV-specific CD8 immunity (see section 9.2.1.2). Similarly, power would be 80% to detect a corresponding decrease in cell-associated RNA (see section 9.2.1.3). The null hypothesis is that the probability is 0.5 (equally likely to observe increase or decrease). For residual viremia (SCA, see section 9.2.1.3), effect size is slightly larger due to anticipated left-censoring below assay limits. From numerical simulation based on a 1-arm t-test (imputing half the lower limit for SCA results below assay limits), power is estimated to be 80% to detect an underlying effect size of 0.67 SD; this 80% power corresponds to assuming that the probability is 0.5 (50%) for a baseline (pre-entry, entry) SCA to be below assay limit compared to 0.75 (75%) after treatment. The assumption that 50% of SCA results will be below assay limits at baseline is supported by findings from ACTG A5276s in which 56% of 668 SCA measurements after 192 and 208 weeks of suppressive ART on 334 **participants** were below assay limits (<1 copy/mL). Analyses will also jointly evaluate efficacy measurements at the multiple post-treatment time points (e.g., the change from baseline to the average of the weeks 16, 24, and 32 measurements [4, 12, 20 weeks on sirolimus]), which could increase statistical power.

9.5 Monitoring

Accrual, baseline characteristics, conduct of the study (including premature treatment and study discontinuations, and reasons, and summaries of sirolimus dosages and trough levels), interruptions of ART >2 days, virologic failures (defined as HIV-1 RNA >200 copies/mL on two consecutive assessments), two consecutive CD4 counts below 300 cells/mm³ (or >50% decrease from study entry) and all reported toxicities and events will be monitored during the study with reports sent to the core team on a regular basis. In addition,

assessment of the availability of stored samples for planned assays will be reviewed regularly. The core protocol team will review the individual safety data frequently (at least monthly) to assess relation of all reported toxicities and AEs to study treatment, including in this assessment the site investigator's opinion on their relation to study treatment as reported on the case report forms.

At the earlier of a) approximately 6 months after the first **participant** begins study treatment and b) after 12 **participants** have reached 12 weeks of study treatment, a Study Monitoring Committee (SMC) will be convened to review the study data and progress according to ACTG Standard Operating Procedures. The SMC will review accrual, **participant** characteristics, AE summaries (and listings detailing each team decision as to the relationship of the AE to study treatment), sirolimus dosages and trough levels (in particular for any **participant** with a Grade 3 or higher AE), CD4+ cell counts and HIV-1 RNA levels/suppression over time, off-treatment and off-study rates (and reasons) and completeness of sample availability. In addition, sirolimus use in all **participants** will be stopped and an SMC safety review will be promptly convened if there are any Grade 4 AEs or greater than three Grade 3 AEs attributed to study treatment in two or more **participants** per section 9.2.1.1. An SMC review will also be triggered if more than 25% of **participants** (evaluating at least 12 **participants**, e.g., greater than 3 of 12) discontinue study treatment due to AEs or other side effects attributable to study drug; the therapeutic duration of the trial might be reduced to 12 weeks or otherwise modified following SMC review. Subsequent SMC reviews will be approximately every 6 months. In addition, the core team or the SMC, at any time it thinks appropriate, may ask for the SMC to independently review all available safety data.

9.6 Analyses

Baseline will be defined as the average of entry and week 12 measurements (or will be based on one if the other is missing).

9.6.1 Primary Analyses

For the primary safety analysis, \geq Grade 3 AEs attributed to study treatment and confirmed CD4+ declines (see section 9.2.1.1) will be summarized. In addition, all other reported AEs \leq Grade 2 attributed to study treatment as well as all reported events \geq Grade 2 (regardless of treatment relatedness) will be summarized. All **participants** who have been exposed to study treatment will be included in the analysis.

For the primary immunologic (see section 9.2.1.2) and virologic (see section 9.2.1.3) efficacy outcomes, post-treatment changes will be evaluated comparing measurements pre-treatment (averaged) to the measurement 20 weeks after starting study treatment, testing the null hypothesis of no difference pre-treatment versus post-treatment using a paired t-test. Log-transformations may be applied for the virologic outcomes. To address anticipated left-censoring of SCA measurements, a value one half the lower assay limit will be imputed. If feasible with the modest sample size, censored-data longitudinal data methods that statistically address the

issue of left-censoring (SCA measurements below assay limits) will also be used to evaluate and estimate treatment effects [59]. Mean and quartile plots will summarize the immunologic and virologic measurements at each visit. Because the aim of this pilot study is to investigate the biologic effects of sirolimus, the analyses will be as-treated, limited to **participants** who have data at baseline and week 32 (20 weeks on sirolimus) and who remained on study treatment and ART (and without virologic failure) through week 32. A supplemental analysis will be based on changes from baseline to the last available time point for a **participant** while on study treatment and ART (and without virologic failure).

If there is evidence that there is a significant difference between the week 0 and week 12 levels of the primary immunologic and virologic efficacy measurements, based on paired t-tests between these two time points, then the primary analysis will instead be based on a comparison of slopes pre- versus post-treatment (see 9.6.2). Both sets of results, from the paired t-test analyses and the comparison of slopes analyses, will be reported in the presentation of the study findings.

9.6.2 Secondary Analyses

Additional analyses of safety will summarize the magnitude of CD4+ cell changes baseline to post-treatment time points (mean, quartiles). Analyses will also summarize the number of **participants** who exhibit on two consecutive measurements HIV RNA >200 copies/mL on conventional assay. Tolerability will be assessed by the number of **participants** who prematurely discontinue study treatment and the reasons for discontinuation.

Analyses of secondary virologic and immunologic outcomes will parallel the primary analyses outlined in section 9.6.1. Graphical approaches will summarize the virologic and immunologic measurements over time. Supplemental analyses will compare the change in the slope-over-time pre-treatment (pre-entry to start of treatment) versus post-treatment (start of treatment through week 20 while on treatment) and also may examine the change from baseline to the average of the week 16, 24 and 32 (4, 12, 20 weeks on sirolimus) measurements. Soluble markers (e.g., IL-6 levels) will be log-transformed.

Analyses will also summarize changes in immunologic and virologic measures after discontinuation of study treatment.

Associations between changes in the various immunologic and virologic measurements will be evaluated using scatterplots and correlations coefficients.

The relationship between anal HPV, particularly HPV 16, and immunological measurements of activation and virological measurements of HIV reservoir size will be correlated.

The effect of study treatment on anal dysplasia will be described by evaluating the change in anal Pap tests after study therapy. Pap tests will be categorized as

normal or abnormal according to standard clinical criteria.

10.0 PHARMACOLOGY PLAN

10.1 Pharmacology Study Design

Pharmacology Objective: To assess the pharmacokinetic (PK) interactions between sirolimus therapy and ARV drug levels.

Sirolimus trough drug levels will be drawn on **participants** 4 days after the initial dose until two consecutive sirolimus levels are within the goal range of 5-10 ng/mL. Once two consecutive levels fall within 5-10 ng/mL (which may be achieved before the 4-week time point after sirolimus is initiated), trough samples will be drawn every 4 weeks until week 32 (see section 6.1.1). Monitoring will be done by individual sites that have or use a laboratory that has a CLIA certification or its equivalent. For safety and ease of dosing, **participants** will be recruited and followed only at medical centers that have rapid sirolimus testing available or are able to ship samples to Quest laboratory for rapid turnaround of results based on liquid chromatography tandem mass spectrometry analysis which enables accurate and consistent measures of levels across study sites. Results should be available within 72 hours if shipped to Quest or local laboratory. Sirolimus dose will not be adjusted until study drug has been taken for a minimum of 1 week.

In addition, samples will be collected and stored for batched analysis of ARV measurements following study completion. ARV trough levels will be collected just prior to initiating sirolimus to serve as baseline evaluations. These samples will be collected just prior to morning dosing. **Participants** will be asked to hold their morning doses to allow trough collections.

10.2 Primary and Secondary Data, Modeling and Data Analysis

Real-time analysis for sirolimus will be used for **participant** monitoring only. Batched sample analysis of ARVs will be performed post-hoc using standardized analytical methods. This monitoring will allow the assessment of the PK of sirolimus therapy on ARV drug levels and evaluate the effects of ARVs on sirolimus levels. These analyses will inform potential required dose adjustments if further clinical trials are planned. However, these levels will not be used to dictate dose adjustment or clinical changes.

Batched analysis of ARVs will be carried out using LC tandem MS. As **participants** will be taking various non-PI ARVs, analysis for ARVs will focus on the most common ARVs prescribed to optimize comparisons (e.g., efavirenz, tenofovir, integrase inhibitors). ARV levels will be compared prior to and following sirolimus initiation and to historical ARV PK data. Sirolimus levels will be compared across ARV regimens and to historical data, if available.

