A5337 is a phase I/II, open label, single arm, pilot study to evaluate the safety of sirolimus and its efficacy with respect to its effects on HIV-1 reservoir size and immune function. This study will assess the effects of sirolimus on HIV-1-specific CD8+ T-cell function, HIV transcription, and residual viral production. Measurement of additional inflammatory markers, immunological studies, and reservoir size will be performed on stored specimens if the initial findings appear promising.

DURATION

44 weeks (12-week pre-sirolimus treatment lead-in period, followed by 20 weeks of sirolimus treatment and an additional 12 weeks off sirolimus treatment).

SAMPLE SIZE

30 participants

POPULATION

HIV-infected men and women ≥ 18 years of age, maintained on suppressive antiretroviral therapy (ART) for ≥ 24 months with CD4+ cell count ≥ 350 cells/mm³.

Participants may not be on a PI-based or cobicistat-based regimen 3 months prior to and at any time after study entry and must remain on ART during sirolimus study treatment.

STRATIFICATION

By class of antiretroviral (ARV) regimen

REGIMEN

- For **participants** on a non-protease inhibitor (PI), non-nucleoside reverse transcriptase inhibitor (NNRTI) regimen, and for those on a non-PI, rilpivirine (RPV) based regimen:

[figure not shown]
Sirolimus 0.025 mg/kg/day initial dose for 20 weeks

- For **participants** who are on an NNRTI regimen with the exception of RPV:

Sirolimus 0.05 mg/kg/day initial dose for 20 weeks.

Dosing will be adjusted based on trough sirolimus concentrations to achieve target concentrations between 5 and 10 ng/mL.

Study Design Schematic

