5.0 STUDY TREATMENT

5.1 Regimens, Administration and Duration

Eligible **participants** will be stratified at study entry by class of ART regimen as follows:

Participants taking a non-PI, non-NNRTI containing regimen, and those on a non-PI, RPV-based regimen, will initially receive:

- Sirolimus 0.025 mg/kg/day administered orally once daily with or without food. See Table 2.

Participants taking an NNRTI containing regimen (with the exception of RPV) will initially receive:

- Sirolimus 0.05 mg/kg/day administered orally once daily with or without food. See Table 3.

In order to achieve therapeutic levels, therapy will be initiated with the dosage noted above and dosing will be subsequently adjusted based on trough blood sirolimus concentrations to achieve target concentrations between 5 and 10 ng/mL (see **Table 4**). A detailed dosing table based on the adjustment algorithm in **Table 4** can be found on the A5337 PSWP.

Table 2. Sirolimus Dosing at 0.025mg/kg			
Weight	Initial daily dose	25% increase*	25% reduction*
50 to 70 kg	1.5 mg	2 mg	1 mg
71 to 90 kg	2.0 mg	2.5 mg	1.5 mg
91 to 110 kg**	2.5 mg	3 mg	2.0 mg

*Dose adjustment based on sirolimus trough level.

**For participants weighing >110 kg, the sirolimus dose needs to be clarified by the team.

Table 3. Sirolimus Dosing at 0.05mg/kg			
Weight	Initial daily dose	25% increase*	25% reduction*
50 to 70 kg	3 mg	4 mg	2 mg
71 to 90 kg	4 mg	5 mg	3 mg
91 to 110 kg**	5 mg	6.5 mg	4 mg

*Dose adjustment based on sirolimus trough level

**For participants weighing >110 kg, the sirolimus dose needs to be clarified by the team.

Table 4. Sirolimus Dose Adjustment Algorithm	
Sirolimus level	Dose adjustment*
<5 ng/mL	Increase dose by 25%,
5-10 ng/mL	Continue current dose
>10, <15 ng/mL	Reduce dose by 25%
>15, <20/ng/mL	Hold dose for 48 hours, then decrease dose by 25%
>20/ng/mL	Hold dose until next level check, if <12 ng/mL, then restart study drug at 50% prior dose

*Round dose up to closest sirolimus 0.5mg tablet. Sirolimus tablets cannot be split, crushed or chewed.

Participants will initiate study treatment at week 12 and continue for 20 weeks.

Participants will be followed off-treatment for an additional 12 weeks for a total of 44 weeks. Treatment must be initiated within 72 hours of week 12 (day 0) evaluations (see section 6.2.3).

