6.3.12 Pharmacokinetic Samples

PK Monitoring of Sirolimus

Trough sirolimus levels (whole blood) will be collected 4 days after administration of the first dose of sirolimus and will be analyzed and reported in real time. Trough samples will then be drawn twice a week (approximately days 4 and 7 of each week) for up to 4 weeks until two consecutive drug levels fall within 5-10 ng/mL. Once two consecutive levels fall within 5-10 ng/mL (which may be achieved before the 4-week time point after sirolimus is initiated), trough samples will be drawn every 4 weeks until study week 32 (see section 6.1.1).

The windows for PK sampling are ± 1 day through week 16 and ± 1 week for weeks 18 through 32.

Stored Plasma for PK Exposure Estimates of ARVs

In addition to real-time sirolimus testing, stored plasma will be collected for batched analysis of ARV drug concentrations.

PK Dosing Restrictions

Participants having PK sampling should be instructed to hold their morning doses of sirolimus and ARVs so a trough sample can be collected. Once trough samples have been collected, **participants** can take their normal morning doses of sirolimus and ARVs. For **participants** taking EFV, the evening dose can be taken and the time of the last dose recorded when **participants** come to the clinic for PK blood draws.

PK Data Collection

For sirolimus and ARV PK collection visits, food intake, and date, time and amount of the last three doses of sirolimus and ARVs will be recorded on the CRF.

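### Protocol 10.2 judges the effect of antiretrovirals on sirolimus by comparing sirolimus levels, but the starting dose is set by regimen class and everyone is titrated to one trough range, so the comparison needs a dose-adjusted measure

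*Protocol*

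**What the plan says.** Protocol 10.2 states that the drug-level monitoring will be used to "evaluate the effects of ARVs on sirolimus levels". The method for that direction of the interaction is one sentence: "Sirolimus levels will be compared across ARV regimens and to historical data, if available". It gives no time point, no summary measure and no use of dose. The same section gives the purpose: "These analyses will inform potential required dose adjustments if further clinical trials are planned". The work belongs to exploratory objective 1.4.1 and exploratory outcome 9.2.3.6.

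Two design features bear on this comparison.

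- **Starting dose depends on ARV class.** Under Protocol 5.1 it is 0.025 mg/kg/day for regimens without an NNRTI and for rilpivirine-based regimens, and 0.05 mg/kg/day for other NNRTI regimens.
- **One target for all.** Protocol 5.1 says "dosing will be subsequently adjusted based on trough blood sirolimus concentrations to achieve target concentrations between 5 and 10 ng/mL". Table 4 raises the dose by a quarter below 5 ng/mL and cuts it by a quarter above 10. Above 20 the rule is "Hold dose until next level check, if <12 ng/mL, then restart study drug at 50% prior dose".

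Protocol 10.1 allows no dose change in the first week. Protocol 2.2.5 expects NNRTIs to lower sirolimus levels and expects upward dosing and level monitoring to compensate.

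Dose data exist. At PK visits, "date, time and amount of the last three doses of sirolimus and ARVs will be recorded on the CRF" (Protocol 6.3.12). Protocol 6.3.4 records every change in sirolimus dosing, and weight at entry and each later visit.

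SAP 14 summarises each participant's average trough in the primary analysis population and correlates it with outcome changes. It does not compare levels between ARV regimens.

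**The concern.** In a concentration-controlled study the concentration is the quantity being held fixed, and the response to a change in clearance is a change in dose. If titration succeeds, NNRTI and other participants end with similar troughs whatever the size of the interaction. A comparison of those troughs then measures how well titration worked.

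Earlier levels have a different fault. Before any adjustment the NNRTI group takes twice the dose per kg, so its levels reflect that doubling as well as any interaction.

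At stake is the use the protocol names, which is dosing in later trials. A level ratio near 1 could be read as no interaction when clearance differs two- or three-fold. An average over all troughs could suggest higher exposure on NNRTIs when there is no interaction at all.

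**Working it through.** The documents give no sample size, power or effect size for this comparison, so there is no stated figure to reproduce.

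**Algebra.** Let r be the true clearance ratio, NNRTI (except rilpivirine) over other, and assume levels are proportional to dose.

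- Level per mg: ratio 1/r at any dose.
- Before titration: level ratio = dose ratio × 1/r = 2/r. For r = 1, 1.5, 2 and 3 this is 2.0, 1.33, 1.0 and 0.67.
- After perfect titration to one target: level ratio = 1 and dose ratio = r, for every r.

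**Simulation, because titration is imperfect.**

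- From the protocol: half-life 62 h (2.1.8); starting doses 2 mg and 4 mg (71-90 kg rows of Tables 2 and 3); Table 4 steps, rounded up to 0.5 mg; no change before day 7; twice-weekly troughs until two consecutive levels are in range, then the later schedule (6.1.1, 6.3.12).
- Assumed: 40% between-participant CV; 20% within-participant variation; reference steady-state trough of 4-8 ng/mL on 2 mg; r of 1, 2 or 3; one compartment, with the same half-life in both classes.

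Geometric mean ratios, NNRTI over other:

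| True effect | True level per mg | Raw, day 7 | Raw, average of all troughs | Raw, end of treatment | Dose-normalised, end of treatment |
|---|---|---|---|---|---|
| None | 1.00 | 2.0 | about 1.25 | about 1.0 | about 1.0 |
| Two-fold | 0.50 | 1.0 | about 1.0 | 0.94-1.00 | 0.50-0.52 |
| Three-fold | 0.33 | 0.67 | about 0.87 | 0.92-0.99 | 0.33-0.35 |

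The end-of-treatment dose ratio is about 2.0 for a two-fold effect and 2.9 for a three-fold effect, so the titrated dose carries the signal that the level has lost.

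**Sensitivity.** With all eight troughs to day 28 taken from everyone, and a between-participant CV of 30% or 50%, the raw end-of-treatment ratio is 0.93-0.99 for a two-fold and 0.91-0.98 for a three-fold effect. The all-trough average is 1.18-1.23 for no effect, 0.95-0.98 for two-fold and 0.85-0.89 for three-fold. Dose-normalised ratios at end of treatment are 0.50-0.51 and 0.33-0.34.

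**Early samples.** The fraction of steady state is 1 − exp(−ln 2 × t / half-life). At 62 h this is 66% on day 4 and 85% on day 7. For 46 to 78 h (62 ± 16) the ranges are 57-76% and 78-92%. Day 4 and day 7 levels escape titration but are not at steady state.

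**Precision of the dose-normalised ratio.** The variance on the log scale is ln(1 + 0.40²) + ln(1 + 0.20²) = 0.148 + 0.039 = 0.188, so the SD is 0.433. The documents do not give the split by ARV class, so two are assumed, with t(28) = 2.048:

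- 15 against 15: SE = 0.433 × √(1/15 + 1/15) = 0.158; a ratio of 0.50 has a 95% CI of about 0.36 to 0.69.
- 5 against 25: SE = 0.433 × √(1/5 + 1/25) = 0.212; the CI is about 0.32 to 0.77.

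These intervals are wide, but both exclude 1.

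**The case against.** The best defence is that Protocol 10.2 is one under-specified sentence about an exploratory objective. It does not say that dose will be ignored, and the protocol collects dose with care and has dosages reviewed beside troughs (9.5). SAP 1 defers exploratory objectives it does not cover. The other direction of the interaction, ARV levels before and after sirolimus, is unaffected. No primary or secondary endpoint or safety rule depends on the sirolimus comparison.

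This limits the importance of the point but does not answer it. The sentence names levels as the thing compared, and neither document names a dose-adjusted alternative. Followed as written, the comparison misleads.

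Two stronger readings should be set aside.

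- **That levels look alike at every time point whatever the interaction.** This holds only after titration. Day 7 ratios run from 2.0 to 0.67, and all-trough averages from about 1.25 to 0.87. Those summaries are shifted by the starting doses, but they do vary with the effect.
- **That SAP 14 makes the same error.** It contains no regimen comparison. Its stated purpose is pharmacodynamic, and for exposure-response the achieved trough is the right measure. Trough per mg reflects clearance, so substituting it there would damage a sound analysis.

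The simulation also follows everyone to the end of treatment, whereas SAP 5.3 reports that 13 of 29 participants had less than 20 weeks of sirolimus. The exact ratios are therefore illustrative. The pattern follows from the algebra.

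**Conclusion.** The point stands for Protocol 10.2. Levels after titration strongly attenuate an ARV effect on sirolimus: a true two- to three-fold effect shows as a ratio of about 0.92-1.00. Levels before titration, and averages that include them, are shifted upward for NNRTI participants by the two-fold starting dose. No effect then shows as about 2.0 at day 7 and 1.25 on average, and a two-fold effect shows as none. Dose-normalised troughs recover the true ratio.

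The half-life and dosing rules come from the protocol. Variability, reference trough, effect sizes, dose proportionality and a common half-life are assumptions. The change is worth making because the result is meant to guide later dosing, but the objective is exploratory and the trial's main conclusions do not depend on it.

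**What to change.** In Protocol 10.2, and in any later analysis plan for objective 1.4.1, compare two measures by ARV class (NNRTI except rilpivirine against all other regimens):

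1. the dose-normalised trough, meaning the level divided by the recorded recent daily dose per kg;
2. the titrated daily dose in mg/kg at a stable in-range trough.

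Report each as a geometric mean ratio with a 95% CI, and state the dose-proportionality assumption. Prefer samples taken after the dose has been stable for some time. At a 62 h half-life the last three daily doses supply only 1 − exp(−ln 2 × 72/62) = 55% of a steady-state trough, so the dose-modification record should confirm stability. Report raw troughs by regimen only as attainment of the target range.

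Leave the SAP 14 summary of achieved troughs and its correlations with outcomes unchanged.

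The cost is wording and a little extra analysis of dose, weight and trough data already collected. The intervals will be wide at this sample size. No dosing rule or visit changes.
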